12.1.1. Hearing AEs of special interest

There are two types of possible hearing impairment AEs – subjective and objective AEs. **Subjective events** will be reported to the AE assessor during their interaction with the subject/family (i.e. hearing impairment associated with spoken language, tinnitus, turning up the TV, functional concerns, etc.). **Objective events** will be identified by the Audiologist during the audiologic evaluation. Objective hearing impairment AEs are identified by assigning a CTCAE or ABR Adverse Event grade at every Audiologic evaluation after screening/baseline. A modified CTCAE scale is used to grade audiologic evaluations obtained through behavioral audiometry. An ABR Adverse Event Scale is used when behavioral audiometry is not obtainable, and an Auditory Brainstem Response test is used to determine hearing thresholds.

August 27, 2018

Page 40

The following is a modified grading system, derived from the CTCAE (v4.03) scale that will be

used to determine the AE grade for hearing impairment when hearing thresholds are obtained

via pure tone audiometry:

Grade 1: (on a 1, 2, 3, 4, 6 and 8 kHz audiogram): Threshold shift >20 dB at 8 kHz in at

least one ear.

Grade 2: (on a 1, 2, 3, 4, 6 and 8 kHz audiogram): Threshold shift >20 dB at 4 kHz and

above in at least one ear.

• Grade 3: (on a 1, 2, 3, 4, 6 and 8 kHz audiogram): hearing impairment sufficient to

indicate therapeutic intervention, including hearing aids; threshold shift >20 dB at 3 kHz

and above in at least one ear; additional speech-language related services indicated.

Grade 4: Decrease in hearing to profound bilateral impairment (absolute threshold >80

dBHL at 2 kHz and above); non-serviceable hearing

The following is the "ABR Adverse Event Scale" (developed specifically for use in VTS301)

that will be used to determine the AE grade for hearing impairment when hearing thresholds

are obtained via diagnostic ABR not using pure tone thresholds:

Grade 1: Threshold shift >10 < 20 dB at 4 kHz in at least one ear

Grade 2: Threshold shift >20 dB at 4 kHz in at least one ear

• Grade 3: Threshold shift >20 dB at 2 kHz in at least one ear

• Grade 4: Absolute thresholds >80 dBeHL from 1-4 kHz (not previously present at

baseline) bilaterally

12.1.2.AE summaries

All AE presentations will summarize treatment emergent adverse events (TEAEs) defined as

adverse events with onset on or after randomization or onset prior to randomization but with

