worsened severity post-randomization. In case of partially missing AE start and stop dates,

the dates will be imputed by comparing to first dose date of study medication so that the

corresponding AEs will be made treatment-emergent whenever possible, unless the available

partial date information clearly indicates that the event happened outside of the treatment

CONFIDENTIAL

period. In general, a conservative strategy will be followed with respect to the assignment of AEs with partial start dates.

Presentations for Part A/B will include all adverse events with an onset date through the first Part C dose date - 1. Presentations for Part C will include all adverse events with an onset date on or after the first VTS-270 dose date. The incidence of TEAEs will be shown in terms of the total number of subjects and not in terms of the total number of events.

The following presentations of treatment-emergent adverse events will be summarized by study part and treatment group:

- Serious adverse events
- All adverse events
- Adverse events by greatest toxicity grade (greatest severity will be used where toxicity grade is missing)
- Adverse events ≥ Grade 3 toxicity (severity will be used where toxicity grade is missing)
- Adverse events related to study drug (i.e., AEs classified as possibly, probably, and definitely related)
- Adverse events related to LP procedure (Adverse events were categorized as 'related to LP procedure' if the event was marked as related to intrathecal procedure or other protocol required procedures.)
- Adverse events of special interest: Related to or resulting in hearing impairment, and seizures, other agitation, aphasia, dystonia and other neurologic AE's.
- Adverse events leading to study discontinuation.

All of the above summaries, other than the AEs related to study drug summary, will be repeated based on related AEs. All AEs will be listed with MedDRA coding, onset and resolution dates, seriousness, severity, relationship, actions, and outcome.

In addition, the adverse events for subjects who took study medication from batch will be summarized to evaluate any impact of the decrease in pH over time.

August 27, 2018

Page 42

The following subgroup analyses will also be performed.

• Treatment emergent adverse events by SOC, PT, and post-baseline Miglustat use (yes,

no)

Treatment related treatment emergent adverse events by SOC, PT, and post-baseline

Miglustat use (yes, no)

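### Objective hearing adverse events are graded on two non-equivalent scales, but the adverse event tables are not split by scale, so any-grade and Grade 3 or higher incidence depends on an unreported mix of tests

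*SAP*

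**What the plan says.** SAP 12.1.1 separates subjective hearing events, reported to the adverse event assessor, from objective ones, to which the audiologist assigns a grade at each evaluation after baseline. Two scales serve the objective events. "A modified CTCAE scale is used to grade audiologic evaluations obtained through behavioral audiometry", whereas "An ABR Adverse Event Scale is used when behavioral audiometry is not obtainable".

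- **Grade 1.** The audiometry criterion opens "Grade 1: (on a 1, 2, 3, 4, 6 and 8 kHz audiogram): Threshold shift >20 dB at 8 kHz in at" and is met by a single ear. ABR: "Grade 1: Threshold shift >10 < 20 dB at 4 kHz in at least one ear".
- **Grade 2.** The audiometry criterion opens "Grade 2: (on a 1, 2, 3, 4, 6 and 8 kHz audiogram): Threshold shift >20 dB at 4 kHz and" and extends to the higher frequencies, again for a single ear. ABR: "Grade 2: Threshold shift >20 dB at 4 kHz in at least one ear".
- **Grade 3.** Audiometry: a shift above 20 dB from 3 kHz upward, with wording on intervention and speech-language services. ABR: a shift above 20 dB at 2 kHz, with no such wording.
- **Grade 4.** Audiometry: bilateral absolute thresholds above 80 dBHL from 2 kHz upward. ABR: bilateral absolute thresholds above 80 dBeHL from 1 to 4 kHz, not present at baseline.

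SAP 12.6 lists the diagnostic ABR frequencies as 500, 1000, 2000 and 4000 Hz. SAP 12.1 summarises the worst grade per subject. SAP 12.1.2 plans, among others, "Adverse events by greatest toxicity grade", events of Grade 3 or higher, and a hearing category among the events of special interest. All are broken down by study part and treatment group only.

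**The concern.** SAP 12.6 names ototoxicity as a known risk of the drug, so the incidence and grade of hearing events are figures that readers will quote. If a subject can be an event on one scale and not on the other with the same hearing change, the pooled figure describes the mix of tests as well as the drug. The test is not assigned at random: a subject reaches the ABR scale because behavioural audiometry could not be obtained. The documents do not say how many subjects or visits that is. Nor do they say how a subject is graded when one test was used at baseline and the other later.

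**Working it through.** The documents state no hearing event rate, so there is no planned figure to reproduce. The check applies both printed scales to the same hearing change.

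**Step 1: same shift, both scales.** One ear, shift criteria only. A frequency and above is read as all tested frequencies from there up.

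| Threshold shift | Audiometry | ABR |
|---|---|---|
| 25 dB at 8 kHz only | Grade 1 | none |
| 30 dB at 6 and 8 kHz | Grade 1 | none |
| 15 dB at 4 to 8 kHz | none | Grade 1 |
| 20 dB at 4 to 8 kHz | none | none |
| 25 dB at 4 to 8 kHz | Grade 2 | Grade 2 |
| 25 dB at 3 to 8 kHz | Grade 3 | Grade 2 |
| 25 dB at 2 to 8 kHz | Grade 3 | Grade 3 |

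The scales disagree on whether there is an event (rows 1 to 3) and on whether it reaches Grade 3 (row 6). If instead any single frequency in the range suffices, 25 dB at 8 kHz alone meets the audiometry Grade 3 shift criterion, and the gap widens.

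**Step 2: the gap at 20 dB.** ABR Grade 1 requires less than 20 dB and Grade 2 more than 20 dB. A shift of exactly 20 dB at 4 kHz has no grade, although 15 dB does.

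**Step 3: how far the rates can differ.** This is an illustration. Assumed: normal error with SD 5 dB on a shift, rounding to 5 dB steps, two independent ears, one visit, ABR judged at 4 kHz and audiometry at 8 kHz. With per-ear probability p, the probability of an event is 1 − (1 − p)².

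- True loss 15 dB, ABR as printed: p = P(12.5 to 17.5) + P(above 22.5) = 0.383 + 0.067 = 0.450, giving 1 − 0.550² = 0.70. If exactly 20 dB were graded, p = 0.691, giving 0.90.
- True loss 15 dB, audiometry: p = P(above 22.5) = 0.067, giving 0.13.
- True loss 30 dB confined to 6 and 8 kHz: audiometry p = 0.933, giving 0.996. ABR sees only noise at 4 kHz, p = 0.006, giving 0.012.
- No true loss: ABR gives about 1% at SD 5 dB. It reaches 6% to 20% only if the SD is 7 to 10 dB (the upper end also grades exactly 20 dB). Audiometry then gives 0.1% to 2.5%.

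A second simulation assumed a mean 8 kHz shift of 15 to 35 dB, SD 15 dB and three slopes across frequency. Any-grade rates, audiometry against ABR, ran from 31% against 42% (nearly flat loss, mean 15 dB) to 80% against 40% (steep high-frequency loss, mean 35 dB). With the middle slope and mean 35 dB, Grade 3 was 38% against 12%. The gap can go either way.

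**Step 4: effect on a pooled rate.** With ABR share f, pooled rate = (1 − f) × audiometry rate + f × ABR rate. The share is assumed to be 10% to 30%.

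- Steep loss: 0.9 × 0.80 + 0.1 × 0.40 = 0.76, falling to 0.7 × 0.80 + 0.3 × 0.40 = 0.68.
- Nearly flat loss: 0.9 × 0.31 + 0.1 × 0.42 = 0.32, rising to 0.7 × 0.31 + 0.3 × 0.42 = 0.34.
- If the true risk difference for loss confined to 6 to 8 kHz were 50 points and ABR detected none of it, the pooled difference would be 50 × (1 − f) = 45 to 35 points.

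**The case against.** The strongest reply is that adverse event grade is not the plan's only measure of ototoxicity, nor its preferred one. SAP 12.6 favours pure tone assessment. It plans thresholds by arm, visit, frequency and ear, a high-frequency average over 4, 6 and 8 kHz, separate ABR thresholds, and severity categories for each test, including a high-frequency one. A reader might infer that high-frequency loss goes unreported; these summaries show otherwise. They do not, however, give event incidence or grade.

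Second, the shift size differs only at Grade 1. Grades 2 and 3 use more than 20 dB on both scales, and Grade 2 nearly agrees. Adding Grades 2 to 4 in the planned greatest-grade table already comes close to a common event. This stands, and it limits the problem to the any-grade and Grade 3 or higher rates.

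Third, a method-specific scale is a reasonable response when audiometry cannot be done, and ABR's frequency range cannot be changed in analysis. This stands too. What can be changed is the reporting.

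Fourth, a reader might infer that the comparison with sham is biased. The documents do not support that: the same rules apply in both arms and no hypothesis test is planned on these tables. If the ABR share differed by chance, a distortion could arise; for example, a 10-point difference in share with a 40-point gap between scales would contribute 0.10 × 40 = 4 points. Nothing in the documents shows such an imbalance.

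Finally, one might infer that these tables bear on dose selection. Hearing was one part of the safety review for that decision, which was already complete.

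**Conclusion.** The point holds as a reporting gap. The two scales are not equivalent at Grades 1, 3 and 4, and the planned tables combine them. The combining is inferred from the absence of any split; no section says it in words. As planned, the any-grade and Grade 3 or higher incidence of objective hearing events cannot be interpreted without knowing the ABR share. Subjective reports in the same special-interest category are unaffected.

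The Step 1 grades follow from the printed rules under the stated reading of the frequency ranges. The size does not follow from the documents: the simulated rates and the 45-to-35-point dilution rest on assumed noise, loss pattern, risk difference and ABR share, and are not estimates for this trial. The change is worth making because it is cheap and concerns a known toxicity. It does not call the efficacy analysis or the between-arm comparison into question.

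**What to change.** In SAP 12.1.2:

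1. Tabulate objective hearing adverse events by grading scale (audiometry, ABR) and treatment group, with the number of subjects tested by each method as denominator. State that loss above 4 kHz is reported only for audiometry-tested subjects.
2. As a supplement to the all-grade table, not a replacement, add one event that both tests can measure: a shift above 20 dB at 4 kHz in at least one ear, from a baseline obtained with the same test.
3. State how an ABR shift of exactly 20 dB at 4 kHz is tabulated.

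This concerns tabulation only and leaves grading at the sites as it is. The cost is SAP wording and two extra descriptive tables from data already collected. The ABR rows will have small denominators. The common event omits isolated 6 to 8 kHz loss, which is why it cannot replace the main table. Subjects without a baseline on the same test drop out of it and should be counted.

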Subjects who complete Part B, meet the criteria for dose reduction for a second time (i.e.,

subjects who do not tolerate 400 mg), or participated in Part B for at least 6 months and

meet the rescue therapy criteria are eligible to participate in Part C.

Subjects enrolled in the National Institutes of Health (NIH) Phase 1/2a study (13-CH-

0001) will also be eligible to participate upon completion of their participation in the

phase 1/2a study.

Subjects who have received prior written authorization from Vtesse to enroll directly into

Part C are eligible to participate.

Part A, Part B and NIH phase 1/2a subjects who transition into Part C will receive treatment

with VTS-270 for up to 3.5 years or until the investigator considers VTS-270 to no longer be

beneficial to the subject, VTS-270 receives marketing authorization, or the development

program is discontinued.

August 27, 2018 Page 16

Further details about Parts A, B, and C can be found in the Protocol.

Device Safety and Tolerability Substudy:

A substudy investigation of the safety and tolerability of the intrathecal port B. Braun Celsite IT Access Port System is being conducted in approximately 6 subjects in European sites who meet the eligibility criteria to have the device implanted for VTS-270 infusion. These subjects will remain in Part C of VTS301.

Exhibit 1 displays the overall study design.

Exhibit 1.	Phase 2b/3	three-pa	rt study desi	gn					
	Part A			Part B			Part C		
Treatment	Dose	N	DSC Assessment	Dose	N	Total	Dose	N	Total
VTS-270	900 mg 1200 mg	3	Final Dose Selection	900 mg ¹	26	35	900 mg biweekly, or lower dose with possible reduced frequency	51 + up to 14 NIH phase 1	Up to
	1800 mg	3							65
Sham	Sham control	3		Sham control	13	16	 		
	Total	12			39	51			

DSC = dose selection committee; NIH = National Institutes of Health

4.2.Study duration, visits and assessments

Total duration of subject participation in Parts A and/or B was approximately 58 weeks, which included the screening period of 45 days, and 52 weeks of IT injections or sham control procedures to be given every 2 weeks. Study visits coincided with study drug administration every 2 weeks. An additional 26 weeks of post-treatment follow-up was included for any subject who elects not to participate in Part C for a total of 182 weeks. Assessments of adverse events, vital signs and concomitant medications occur throughout Part C with study

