n (%)	n (%)	n (%)	P-VALUE

Second, the results will be presented by treatment group, stratified by Part A vs. Part B. The layout will be presented similar to that shown below:

Part A	Part A	Part B	Part B
Sham	Treatment	Sham	Treatment
(N=X)	(N=X)	(N=XX)	(N=XX)
n (%)	n (%)	n (%)	n (%)

Additionally, all formal statistical analyses will be stratified by whether subjects were randomized into Part A vs. randomized into Part B.

For Part C, all table presentations will display results by path of entry (e.g., Part A/B Sham, Part A/B Treatment, Part C) and overall.

In addition to tabular summaries, all relevant electronic case report form (eCRF) data and external lab data will be provided in by-subject listings. All data listings, summaries, figures, and statistical analyses will be generated using SAS Version 9.4 or higher [3].

8.1.Study days

For the purpose of the analysis, the reference time (time zero) is defined as the start date/time of study drug administration for all purposes, except for the age and concomitant medication where time zero is the time when Informed Consent was granted. Randomization may occur on or before Study Visit 1 (Day 0). Protocol-defined Day 0 is the calendar date of the first administration of the study drug. Study day will be calculated relative to first administration of the study drug. Specifically:

Study day = date of visit/test/procedure – first dose date + 1.

Statistical analyses will be performed using study day as defined above. Protocol study day =

Study day if study day < 0; or (Study day - 1) if Study day ≥ 0 . All data listings will be based

on the Study day as defined above.

8.2.Baseline

The baseline value for all NPC-SS related endpoints will be based on the assessment

performed at screening. The baseline value for all other study assessments including but not

limited to vital signs, clinical outcome and disease progression measures, and concomitant

medications is defined as the last non-missing value prior to the first dose, unless otherwise

specified.

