- Individual level outcomes applied to each of the NPC-SS composite domains following 52 weeks of treatment for VTS-270 treated subjects compared to sham controls. Each individual level outcome will be assigned the value of +1 if the change from baseline is negative (i.e., the subject improves over time), 0 if the change from baseline is 0, and -1 if the change from baseline is positive (i.e., the subject declines over time). The analysis of the individual-level outcome will be based on the exact likelihood ratio test to test the null hypothesis that the values are the same across the two groups. The analysis will be applied to each of four composite domains of the NPC-SS scores separately.
- The proportion of subjects that are responders (defined as a score of 0 or +1) on each
 domain (ambulation, cognition, fine motor, swallowing) of the NPC-SS composite will
 be analyzed using the CMH test, stratified by study part.

 Cross-tabulation analysis of Clinician CGIC responders (defined as a score of no change, minimally improved, moderately improved, or markedly improved) and individual NPC-SS composite domain responders (defined as no change or improvement) at Week 52.

11.7.Subgroup analyses

Subgroup analyses will be performed on the following efficacy endpoints:

- Change from baseline in NPC-SS composite score at Week 52
- Blinded Clinician CGIC at Week 52
- Change from baseline in NPC-SS total score at Week 52
- Change from baseline in NPC-SS total score minus hearing and ABR at Week 52
- Change from baseline in individual scores for the 9 domains of the NPC-SS score at Week 52
- Composite NPC-SS mean annualized rate of change (slope) from baseline at Week 52

The endpoints above will be summarized by treatment group for the subgroups defined on the basis of the categorized variables listed below:

Grouping variable	Subgroups
Baseline Miglustat use	Yes,
	No
Baseline NPC severity	<20,
	≥20
Duration of neurological	<4,
symptoms at baseline (years)	4-8,
	>8
Post-baseline Miglustat use	Yes,
	No
Clinician-CGIC severity	Minimally worse,
	Moderately worse,

	Markedly worse

12. Safety summaries

All of the assessments in the sections below will be performed both for Part B using the Safety population and Part C using the Part C Open-Label population.

12.1.Adverse events

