Neurological examination ^f	X													X	
Clinical laboratory testing ^g	X							X						X	
12-lead ECG	X														
Audiologic testing	X	X	X#	X#	X#	X				X				X	
Auditory brainstem response	X					X#									

August 27, 2018 Page 50

Visit Number		1	2	3	4	5	6	7	8	9	10	11	12	13	14
Study Day	Day -45 to Day -1	0	14	28	42	56	70	84	98	112	126	140	154	168	182
Window (days)			(±3)	(±3)	(±3)	(±3)	(±3)	(±7)	(±7)	(±7)	(±7)	(±7)	(±7)	(±7)	(±7)
Time Point (Week)	Screening	1 st Study Dose	2	4	6	8	10	12	14	16	18	20	22	24	26
NPC Clinical Severity Intake	X	X				X				X				X	
Clinician-CGIC ^h and Caregiver-CGIC		X				X				X				X	
TUG Test		X				X				X				X	
9-Hole Peg Test		X				X				X				X	
EQ-5D-3L QoL		X				X				X				X	
Confirm subject eligibility		X													
Randomizationi		X													
Collect plasma biomarker samples ^j		X				X#		X						X	
Sham or lumbar puncture and study drug administration		X	X	X	X	X	X	X	X	X	X	X	X	X	X
Collect CSF samples (study drug subjects only)		X				X#		X						X	
Collect whole blood for genetic testing		X													
Adverse events ^k		X	X	X	X	X	X	X	X	X	X	X	X	X	X
Concomitant medications		X	X	X	X	X	X	X	X	X	X	X	X	X	X

CGIC = Clinical Global Impression of Change; CSF=cerebrospinal fluid; ECG = electrocardiogram; hx=history; NPC = Niemann-Pick disease, type C; NPC1=Niemann-Pick disease, type C1; QoL=quality of life; TUG=timed up and go

 $^{^{\}rm a}$ Medical history includes history of NPC1 disease, diagnosis date, and prior treatments.

^b Urine will be obtained for urinalysis and biomarker testing

August 27, 2018

Page 51

^c Full physical exam at Screening; abbreviated physical exam at all other visits.

 $^{^{}m d}$ Vital signs, including blood pressure, will be recorded following a 5-minute rest in supine position.

^e A second set of vital signs will be recorded following recovery of sedation from lumbar puncture or sham procedure.

 $^{^{}m f}$ Full, videotaped neurological exam at Screening and Week 52; brief, videotaped neurological exam at Week 24.

^g Clinical laboratory tests include chemistry, hematology, and coagulation.

^hBlinded Clinician to meet with subject and assess overall status and functionality that will form baseline for future Clinician-CGIC assessments.

ⁱ Randomization may occur on or before Study Visit 1, Day 0, after receipt of NPC Clinical Severity Score from central rater to confirm eligibility.

^j Plasma samples for biomarkers should be obtained prior to intrathecal or sham treatment.

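### The treatment-emergent AE definition is anchored on randomisation, which does not fit the SAP's first-dose time zero in Parts A/B, has no reference date for Part C subjects never randomised, and is not reconciled with the separate Part C presentation rule

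*SAP*

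**What the plan says.** SAP 12.1.2 states that every AE presentation summarises TEAEs, defined as "adverse events with onset on or after randomization or onset prior to randomization but with" "worsened severity post-randomization". Onset and worsening are therefore both judged from randomisation.

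Other parts of the SAP use the first dose:

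- SAP 8.1: "the reference time (time zero) is defined as the start date/time of study drug administration for all purposes", with exceptions only for age and concomitant medication.
- SAP 12.1.2, partial AE dates: "the dates will be imputed by comparing to first dose date of study medication so that the" events become treatment-emergent where possible.

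On timing, SAP 13.2, Exhibit 2, footnote i says "Randomization may occur on or before Study Visit 1, Day 0", and SAP 8.1 repeats this. Footnote k starts AE collection at informed consent.

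SAP 12 applies its summaries to Part B using the Safety population and to "Part C using the Part C Open-Label population". SAP 6.5 requires only one Part C dose for that population. SAP 4.1 admits to Part C "Subjects enrolled in the National Institutes of Health (NIH) Phase 1/2a study" and subjects whom the sponsor authorises to enrol directly.

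SAP 12.1.2 then gives two presentation windows. Part A/B takes AEs with onset up to the day before the first Part C dose. Part C takes AEs with onset from the date of the first VTS-270 dose; this sentence does not say first Part C dose.

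**The concern.** A TEAE definition should separate events before exposure from events after it. In Parts A/B this one starts at randomisation, so events that neither the drug nor the procedure could have caused may be tabulated as treatment-emergent.

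In Part C the reference date does not exist for subjects who were never randomised in VTS301. For those who were, it lies up to a year before the open-label phase began. The Part C window is a second rule with a different anchor, and the SAP does not say how the two combine.

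What is at stake is which events appear in the long-term safety tables. SAP 8 shows Part C by path of entry, and SAP 12.1.2 names hearing impairment and seizures as events of special interest. Hearing AEs are graded repeatedly (SAP 12.1.1), so worsening of an existing event matters as much as new onset.

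**Working it through.** No figure in the plan depends on this definition, so there is none to reproduce. The check applies the rules to each kind of event and then sizes the groups concerned.

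**Events under the rules as written**

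| Event | TEAE definition (12.1.2) | Presentation window (12.1.2) | SAP 8.1 time zero |
|---|---|---|---|
| A/B subject, onset after randomisation and before first injection or sham, later dosed | Treatment-emergent | Inside A/B (no lower bound) | Before treatment |
| NIH or direct entrant, onset after first Part C dose | Undefined: no randomisation date | Inside Part C | After treatment start |
| A/B active-arm subject, onset during Part B | Treatment-emergent | Inside A/B and, read literally, also Part C, since onset follows the first VTS-270 dose | After treatment start |
| Sham subject, onset on sham, worse after first Part C dose | Treatment-emergent by onset | Inside A/B; outside Part C | Not addressed |
| Direct entrant, onset before Part C, worse after first Part C dose | Undefined | Outside Part C | Not addressed |

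The last two rows assume that worsening is not recorded as a new event; the text available does not settle this. The third row is uneven across paths of entry. Up to 52 weeks of Part A/B events could enter the Part C tables for former active-arm subjects, and none for former sham subjects, whose first VTS-270 dose is their first Part C dose. For NIH entrants, the first VTS-270 dose could fall in the earlier study.

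**Part A/B gap**

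- Minimum: 0 days, since Exhibit 2 marks randomisation at Visit 1.
- Maximum: less than the 45-day screening limit (SAP 4.1), since the central severity score must come first (Exhibit 2, footnote i).
- Share of counted time, gap/(gap + 364), with Week 52 at Day 364: for an assumed 14 days, 14/378 = 3.7%; at the unreachable ceiling, 45/409 = 11.0%. These are shares of time, not of events.

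**Part C subjects without a randomisation date**

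- Exhibit 1: up to 14 NIH subjects added to 51, so 14/65 = 21.5%.
- If all 54 randomised subjects (SAP 8.5) entered Part C: 14/(54 + 14) = 14/68 = 20.6%.
- Direct entrants come on top; their number is not given.

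**Sham subjects who could carry an event into Part C:** 16 planned (Exhibit 1).

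**The case against.** The strongest reply is that the Part C window needs no randomisation date. A reader of the TEAE sentence alone might infer that never-randomised subjects can have no treatment-emergent events, that their AE columns would be empty, and that long-term incidence would be understated. The documents do not support this. The window sentence covers these subjects, and new onsets after their first dose would be presented. Nor is 14 of 65 the size of an error: it counts subjects without a reference date, not events lost. This reply stands.

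For Parts A/B, the reply is that the effect is minor. Exhibit 2 schedules randomisation at the first-dose visit, and undosed subjects are outside the Safety population (SAP 6.4). Pre-dose events should arise about equally in both arms, so the risk difference barely moves and a ratio shifts only slightly toward 1. SAP 12.1 names no formal AE test, related events are tabulated separately, and all AEs are listed with onset dates. Over-inclusion is also the cautious direction for safety. This stands as to size. It does not remove the conflict with SAP 8.1.

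The partial-date rule is weak evidence of harm. An event imputed to the first-dose date is treatment-emergent under either anchor. The rule does show that first dose was the working reference elsewhere in the same paragraph.

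For sham crossovers, new onsets after first active exposure are captured. Only worsening of earlier events is exposed, and only if AE recording does not open a new event.

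**Conclusion.** The point holds as a definitional defect with three parts.

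1. **Parts A/B.** Events between randomisation and the first injection or sham procedure count as treatment-emergent, against SAP 8.1. The effect is probably small and affects both arms. Its size depends on a gap that the documents do not state.
2. **Part C definition.** TEAE status is undefined for up to 14 of 65 planned subjects, plus an unstated number of direct entrants. Their events still reach the tables.
3. **Part C window.** It is not reconciled with the TEAE definition. Read literally, it over-includes Part A/B active-arm events. Because it covers onset only, it misses events from the sham period or from before Part C that worsen after the first Part C dose. The miss assumes that worsening is not entered as a new AE.

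The two Part C window errors run in opposite directions, so the documents do not support a claim that incidence is biased one way overall.

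**What to change.** In SAP 12.1.2:

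- Define Part A/B TEAEs as onset, or worsening in grade, on or after the first VTS-270 injection or sham procedure and before the first Part C dose.
- Define Part C TEAEs as onset, or worsening in grade, on or after the first Part C dose of VTS-270, whatever the path of entry.
- In the Part C window sentence, replace the first VTS-270 dose date with the first Part C dose date.
- List events between randomisation and first dose separately as pre-treatment.

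The cost is SAP wording and one derivation rule. The onset and dosing dates are already collected. The only downside is slightly lower Part A/B counts.
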